3.4.7.1.2. Adverse Event of Special Interest

Adverse events of special interest will also be summarized by assigned region (buttock or thigh) and overall.

3.4.7.2. Study Drug Exposure

The exposure summary will be summarized by assigned region (buttock or thigh) and overall, and will include:

- number of treatment sessions
- whether all 24 injections were completed within each treatment session
- reason that treatment session was not done
- number of injections within each treatment session
- number of dimples treated within each treatment session
- average number of injections per dimple within each treatment session

A listing of subjects who did not receive all 3 treatment sessions and a listing of subjects who did not receive all 24 injections at each treatment session will be generated.

The similar analyses will be done for each treatment area (ie, right side or left side of treatment region) within treatment session. The number of injections should be 12 for a treatment area.

3.4.7.3. Body Weight

Body weight at baseline and post-baseline visits ie, Day 22, Day 43, Day 90, and Day 180 (EOS/ET) will be summarized by assigned region (buttock or thigh) and overall. The summary of change from baseline at postbaseline visits will also be provided.

3.4.7.4. Vital Signs

Vital signs at baseline (Day 1 pre-injection), all study visits (Day 22 pre-injection, Day 43 pre-injection, Day 90, and Day 180 (EOS/ET)), and change from baseline will be summarized by assigned region (buttock or thigh) and overall.

Vital signs on injection days will be summarized at baseline (pre-injection on that day), all postinjection time points (15 minutes and 30 minutes) and change from baseline. The baseline value will be based on the pre-injection measurement at each treatment session.

The incidence of subjects with sponsor-defined potentially clinically importance (PCI), vital sign values (see [Table 5](#)) at any time during the study (including post-30 minute measurements) will be summarized by assigned region (buttock or thigh) and overall. For vital signs PCI calculation, the baseline refers to the latest vital sign assessment values before the first injection on Day 1. Any subject with at least one PCI vital sign value will have all vital sign values listed.

3.4.7.5. Clinical Laboratory

Clinical laboratory results (hematology and chemistry only) at baseline, Day 180 (EOS/ET), and change from baseline will be summarized. Any hematology or chemistry lab results not reported as a continuous value will not be included in the summaries. All post-injection laboratory values

(Day 180 (EOS/ET) and unscheduled labs (taken on Day 1 or later) will be used to determine the incidence of PCI laboratory values.

The incidence of subjects with sponsor-defined PCI laboratory values (see [Table 6](#)) will be presented. Any subject with at least one PCI laboratory value will have all the values for that analyte listed. Individual subject listing of all lab results will be generated.

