14.7. Clinical Laboratory Determinations

Clinical laboratory tests will be conducted according to the Schedule of Events (section 5). Clinical laboratory tests will be performed by a designated central laboratory. Each site will be provided with instructions on specimen collection, preparation, packaging and transport. Refer to the central laboratory manual for further information regarding sample collection, handling, and labeling. The results of the tests will be returned to the investigational sites.

Clinical laboratory test data will be reviewed by the Investigator, or designee, and additional clinical laboratory tests may be ordered at his/her discretion (eg, if the results of any clinical laboratory test falls outside the reference range or clinical symptoms necessitate additional testing to ensure safety). Any additional testing will be performed by the designated central laboratory. The Investigator or qualified designee must acknowledge the review of laboratory results.

The Investigator will review all abnormal lab results for potentially clinically important. Any abnormal clinical laboratory test result meeting the Investigator's criteria for potentially clinically important (refer to central laboratory manual) will be recorded as an AE or SAE as appropriate (see section 14.1.1, Adverse Events, and section 14.1.2, Serious Adverse Events).

Laboratory results will be sent electronically to Endo Pharmaceuticals Inc. for data management.

Clinical laboratory parameters that will be measured in this study are listed in Table 8.

Table 8: Clinical Laboratory Tests

Hematology	Biochemistry	Urinalysis
Hemoglobin	Glucose	Glucose
Hematocrit	Sodium	Protein
Red blood cell	Potassium	Specific gravity
White blood cell (WBC)	Calcium	pH
Platelets	Chloride	Ketones
WBC Differential	CO ₂	Bilirubin
	Inorganic phosphate	Urobilinogen
	Blood urea nitrogen	Nitrite
	Creatinine	Blood*
	Creatinine clearance (estimated)	Leukocytes ^a
	Aspartate transaminase (AST)	
	Alanine transaminase (ALT)	
	Gamma-glutamyl transferase (GGT)	
	Total bilirubin (TBL) (direct bilirubin reflex if elevated)	
	Albumin	
	Alkaline phosphatase (ALP)	
	Uric acid	

^a Microscopic examination will be performed if blood or leukocytes are detected by dipstick.

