17.6.6. Clinical Laboratory Parameters

Descriptive statistics for clinical laboratory values in International System of Units (SI units) and changes from baseline at Day 180 will be presented for each clinical laboratory parameter. Listings for clinical laboratory values for all subjects will be provided.

The number and percentage of subjects with potentially clinically important (PCI) post-baseline clinical laboratory values will be tabulated. The criteria for PCI laboratory values will be detailed in the Statistical Analysis Plan (SAP). The PCI percentages will be calculated relative to the number of subjects with at least one post-baseline assessment. A supportive listing of subjects with post-baseline PCI values will be provided, including the subject ID, study center, baseline and post-baseline values.

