3.2.6.2. Vital Signs and Clinical Laboratories

3.2.6.2.1. Baseline Values and Change from Baseline Values

The baseline values for vital signs and clinical laboratories will be the last available measurement prior to the first dose of study medication. For clinical laboratories this could be the screening value or it could be an unscheduled lab, if the unscheduled lab is the closest value preceding the first injection. For vital signs, baseline will be Day 1 pre-dose for the by visit analyses.

Vital signs will additionally be analyzed on each injection day. For the first treatment session, baseline will be the last available measurement prior to the injection (Day 1 pre-dose). For Day 22 and Day 43, baseline will be the last available pre-injection measurement taken on that day.

Change from baseline will be the visit/time point value minus the baseline value.

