3.2.6.2.3. Sponsor-Defined Potentially Clinically Important Laboratory Values

Table 6 presents the criteria for determining PCI laboratory values.

Table 6: Sponsor-Defined Potentially Clinically Important Laboratory Criteria

Analyte	PCI Low: Less than or equal to	PCI High: Greater than or equal to
Hemoglobin (g/L)	100	190
Hematocrit	0.3	0.6
Platelets (10 ⁹ /L)	100	650
ALT (U/L)		3xULN ^a
AST (U/L)		3xULN ^a
Creatinine (μmol/L)		300
BUN (mmol/L)		12

^a ULN=Upper limit of normal.

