3.5. DERIVED VARIABLES

3.5.1. Subject Level Variables

The following variables will be determined for each subject (see [Table 7](#)).

Table 7: Subject Level Derived Dataset Variables

Variable	Definition
Age Group	≥ 18 to < 35 years ≥ 35 to < 45 years ≥ 45 to < 55 years ≥ 55 to < 65 years ≥ 65 years
Height (cm)	If height unit is inches, then height is equal to the recorded value multiplied by 2.54. And then rounded to 1 decimal point.
Weight (kg)	If weight unit is pounds, then weight is equal to the recorded value multiplied by 0.454. And then rounded to 1 decimal point.
BMI (kg/m ²)	$\text{Weight}/(\text{Height})^2$
BMI Group	Underweight (< 18.5 kg/m ²) Normal Weight (≥ 18.5 to < 25.0 kg/m ²) Overweight (≥ 25.0 to < 30.0 kg/m ²) Obese (≥ 30.0 kg/m ²)
Date of First Injection	Day 1 visit date
Last date in study	Date of last visit where subject was seen by Investigator. If subject was lost to follow-up, then last date of contact. If the subject had contact with the site after the final visit (eg, to follow-up on an AE), the last visit date will still be used as last date in the study.
Time in Study	Last date in study minus Date of first injection + 1
Age at EFP Symptom Onset	(Start date of EFP symptom onset (from medical history) – Date of Birth)/365.25, truncated to integer value. See section 3.5.3 for handling of partial or unknown EFP symptom onset dates.

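### The lab PCI rule defines unscheduled post-injection samples by date, so a Day 1 pre-injection sample can be both the baseline and a counted PCI value

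*SAP*

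**What the plan says.** Four provisions bear on this.

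- **PCI numerator (SAP 3.4.7.5).** The sentence opens with "All post-injection laboratory values" and then lists the sources: the Day 180 (EOS/ET) visit, and "unscheduled labs (taken on Day 1 or later) will be used to determine the incidence of PCI laboratory values".
- **Laboratory baseline (SAP 3.2.6.2.1).** Baseline "will be the last available measurement prior to the first dose of study medication". For laboratories this is the screening value, or "it could be an unscheduled lab, if the unscheduled lab is the closest value preceding the first injection".
- **Criteria (SAP 3.2.6.2.3, Table 6).** The limits are absolute, for example haemoglobin at or below 100 g/L or at or above 190 g/L. No change from baseline is required.
- **Protocol 17.6.6.** "The number and percentage of subjects with potentially clinically important (PCI) post-baseline clinical laboratory values will be tabulated". The denominator is subjects with at least one assessment after baseline.

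Laboratory samples are scheduled only at screening and Day 180 (SAP 3.1.15), so any Day 1 laboratory sample is unscheduled. Protocol 14.7 provides for such samples: "additional clinical laboratory tests may be ordered at his/her discretion (eg, if the results of any clinical laboratory test falls outside the reference range", among other reasons.

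**The concern.** The PCI table is meant to describe laboratory values after exposure. The date condition does not separate the part of Day 1 before the injection from the part after it, so an abnormality present before any drug was given could be tabulated as a post-injection finding. Safety is the primary objective and there is one arm, so no control column would show the same artefact. Only one post-treatment laboratory sample is scheduled, and the count is likely to be low, so one or two misplaced subjects would be noticeable.

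**Working it through.** The plan states no figure to reproduce here. The check is to apply the rules to one sample and then work out what each affected subject contributes.

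**Step 1: can one sample meet both rules?**

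- SAP Table 7 (section 3.5.1) defines the date of first injection as the "Day 1 visit date". A sample drawn that day before the injection is therefore dated Day 1.
- Baseline rule (3.2.6.2.1): if it is the last sample before the first injection, it is the baseline.
- PCI rule (3.4.7.5): it is unscheduled and dated Day 1 or later, so it satisfies the date condition.
- Protocol 17.6.6: it is the baseline, so it is not post-baseline and should not be counted.

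The SAP's date condition admits the sample. The opening words of the same sentence, and the protocol, exclude it.

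**Step 2: does anything later remove it?**

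For vital signs, Table 5 requires both a limit and a change from baseline. A baseline value has a change of 0 from itself and can never qualify. Table 6 has no such second condition, so a laboratory baseline value can qualify.

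**Step 3: a constructed subject (all values assumed).**

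| Sample | Haemoglobin | Baseline? | Meets the date rule? | Collected after injection? |
|---|---|---|---|---|
| Screening | 105 g/L | no | no | no |
| Day 1, unscheduled, before injection | 98 g/L | yes | yes | no |
| Day 180 | 110 g/L | no | yes (scheduled) | yes |

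Under the date rule she counts as PCI low, because 98 ≤ 100. Restricted to samples collected after the first injection, only 110 g/L remains and she is not counted. If her Day 180 value were instead 99 g/L, she would count under either rule and the Day 1 sample would add nothing.

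**Step 4: size per affected subject.**

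With *k* subjects wrongly counted among *N* in the denominator, the incidence rises by 100 × *k*/*N* percentage points. The planned maximum is *N* = 150 (Protocol 17.1, SAP 3.7). The smaller denominators are assumptions.

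| *k* | *N* = 150 | *N* = 120 | *N* = 100 |
|---|---|---|---|
| 0 | 0 | 0 | 0 |
| 1 | 0.67 | 0.83 | 1.00 |
| 2 | 1.33 | 1.67 | 2.00 |
| 3 | 2.00 | 2.50 | 3.00 |

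The documents give no value for *k*.

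**The case against.** The best defence is that the opening words of SAP 3.4.7.5 govern and the bracket only says where post-injection values come from. Read whole, the sentence excludes a pre-injection sample. This stands as evidence of intent, and a reader who infers that the SAP deliberately counts pre-dose values would be wrong. It does not cure the text. The bracket is the condition a programmer would code, and it is wider than the words it is meant to spell out.

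The second defence is rarity, and it stands. Inclusion criterion 5 requires good health on the screening laboratory profile, and exclusion criterion 1e bars clinically significant laboratory abnormalities. Additional tests go to the central laboratory, so a recheck meant to settle eligibility would more naturally fall within screening. Protocol 14.7 allows extra tests but does not mention Day 1. The documents therefore do not show that a Day 1 recheck is the usual use of an unscheduled lab.

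Four stronger readings are tempting and are not supported:

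- **That the error always inflates the table.** SAP 3.5.5.1 counts each subject once, so a subject with a PCI value after dosing is counted anyway.
- **That a particular inflation can be predicted.** Any figure beyond the per-subject effect needs an assumed *k*.
- **That Table 6 is itself wrong.** The protocol asks for a limit and a change for vital signs (17.6.5) but leaves the laboratory criteria to the SAP (17.6.6). Absolute limits are a permitted choice.
- **That collection times are unavailable.** SAP 3.5.3 names times for injections and only dates for laboratory samples, but that section concerns partial dates and does not settle what is recorded.

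Finally, all values of a flagged analyte are listed, so an attentive reader could spot a pre-dose value. The tabulated incidence would still be wrong.

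**Conclusion.** The point holds as a conflict in wording with a small and possibly nil effect. As written, the date condition in SAP 3.4.7.5 lets one Day 1 pre-injection sample be both the baseline and a counted post-injection PCI value, contrary to the sentence's own opening and to Protocol 17.6.6. A subject is miscounted only if all of the following hold: an unscheduled sample is drawn on Day 1 before injection, it breaches a Table 6 limit, the subject was still judged eligible, and she has no PCI value after dosing. Each such subject adds 0.67 percentage points at *N* = 150. It is worth correcting because the table serves the primary objective in a single-arm study and the correction costs almost nothing.

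**What to change.** **Required.** In SAP 3.4.7.5, replace the bracketed date condition on unscheduled labs with *taken after the first injection*, decided by collection time for samples dated Day 1. Add that a sample used as baseline is never counted as post-injection. It would help to state in advance how a Day 1 sample with no recorded time is handled. The cost is one or two sentences and one programming condition. No new data are needed: the baseline rule in 3.2.6.2.1 already requires knowing whether a Day 1 sample preceded the injection.

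**Optional.** Alongside the existing PCI table, show how many PCI subjects already met the same Table 6 limit at baseline. This would let a reader separate pre-existing abnormalities from new ones without changing Table 6. The cost is one extra row or column.

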3.4.7.6. Immunogenicity

Anti-AUX-I and anti-AUX-II titer levels will be summarized at Day 1, Day 22, Day 43, Day 90, and Day 180 (EOS/ET) by assigned region (buttock or thigh) and overall using appropriate descriptive statistics. In addition, a subset of these immunogenicity samples will be analyzed for neutralizing antibodies by calculating the frequency count of the positive samples and the negative samples and the percentage of samples in each category.

Individual subject listing of all immunogenicity results will be generated.

3.4.7.7. Prior and Concomitant Medications

Prior and Concomitant medications will be summarized for preferred term (generic name from WHO dictionary) by assigned region (buttock or thigh) and overall. If two medications are coded to the same preferred term, it will be counted only once for a subject. Medications will be ordered alphabetically by drug class and preferred term within drug class.

Individual subject listing of prior and concomitant medications will be generated.

3.5. DERIVED VARIABLES

3.5.1. Subject Level Variables

The following variables will be determined for each subject (see [Table 7](#)).

Table 7: Subject Level Derived Dataset Variables

Variable	Definition
Age Group	≥ 18 to < 35 years ≥ 35 to < 45 years ≥ 45 to < 55 years ≥ 55 to < 65 years ≥ 65 years
Height (cm)	If height unit is inches, then height is equal to the recorded value multiplied by 2.54. And then rounded to 1 decimal point.
Weight (kg)	If weight unit is pounds, then weight is equal to the recorded value multiplied by 0.454. And then rounded to 1 decimal point.
BMI (kg/m ²)	$\text{Weight}/(\text{Height})^2$
BMI Group	Underweight (< 18.5 kg/m ²) Normal Weight (≥ 18.5 to < 25.0 kg/m ²) Overweight (≥ 25.0 to < 30.0 kg/m ²) Obese (≥ 30.0 kg/m ²)
Date of First Injection	Day 1 visit date
Last date in study	Date of last visit where subject was seen by Investigator. If subject was lost to follow-up, then last date of contact. If the subject had contact with the site after the final visit (eg, to follow-up on an AE), the last visit date will still be used as last date in the study.
Time in Study	Last date in study minus Date of first injection + 1
Age at EFP Symptom Onset	(Start date of EFP symptom onset (from medical history) – Date of Birth)/365.25, truncated to integer value. See section 3.5.3 for handling of partial or unknown EFP symptom onset dates.

3.5.3. Imputation of Partial Dates

Study visit dates, birthdates, informed consent date, injection dates/times, all assessment dates, all lab dates, and date of completion/last contact date must be complete dates; no imputations will be done. No imputations will be done for partial medical history onset/resolution dates (except EFP onset date), partial alcohol/tobacco stop dates, partial AEs onset/end dates and partial concomitant medication start/stop dates. All AEs with a missing onset day will be considered treatment emergent except if the onset month/year is prior to the first injection date. All medications with a missing onset and stop day will be considered concomitant except if the stop month/year is prior to the first injection date.

For EFP onset date and prior EFP medications/treatment dates, missing EFP onset dates or missing prior EFP medication/treatment start dates will be imputed with the 1st day of the month and missing onset month will be imputed with January. If the EFP onset date is indicated as completely unknown but starting less than 5 years ago, the EFP onset date will be imputed as the informed consent date minus 5 years. If the EFP onset date is indicated as completely unknown but starting more than 5 years ago, the EFP onset date will not be imputed. Missing EFP medication/ treatment end days will be imputed with the last day of the month and missing end

months will be imputed with December, except if the end year is equal to the date of injection year and then the EFP medication/treatment end date will be imputed with the first injection date.

All the missing date imputation will be used for the summary tables only; no imputation will be applied for the subject listings.

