
Investigational Product, Dosage and Mode of Administration: EN3835, 1.68 mg, subcutaneous. A dose of 0.84 mg of EN3835 per treatment area will be administered as 12 subcutaneous injections (0.3-mL injection administered as three 0.1-mL aliquots per injection) in each of two treatment areas for a total dose of 1.68 mg and a total volume of 7.2 mL (3.6 mL per treatment area). Total number of injections will be 24 injections per treatment visit into the assigned region (left and right buttocks or left and right posterolateral thighs). There will be 3 treatment visits at 21-day intervals, ie, treatments on Days 1, 22, and 43 will be administered.

Duration of Study: Up to 194 days (includes screening phase)
 
Screening Phase: Up to 14 days

Name of Sponsor/Company: Endo Pharmaceuticals Inc.
Name of Investigational Product: EN3835
Name of Active Ingredient: Collagenase clostridium histolyticum

Criteria for Evaluation:
 
Safety:
 
Safety will be assessed throughout the study through the recording of:
 
 • Adverse events (AEs) (including those of special interest (AESI); which are adverse events such as [REDACTED]) • Vital signs • Clinical laboratory tests • Immunogenicity assessment (ie, assessed through the determination of binding and neutralizing anti-AUX-I and anti-AUX-II antibody levels) 
In addition, injection site reactions/local tolerability in the treated areas (through subject and Investigator reporting) will be assessed.
 
Effectiveness:
 
 • Investigator using the CR-PCSS by live assessment: 5-level scale ranging from 0 (no cellulite) to 4 (severe cellulite) (Day 1 (Baseline) and Days 22, 43, 90, and 180) for each treatment area • Subject satisfaction with cellulite treatment assessment: 5-level scale ranging from 2 (very satisfied) to -2 (very dissatisfied) (Day 180)

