14. ASSESSMENT OF SAFETY

14.1. Definitions

14.1.1. Adverse Events

An adverse event (AE) is any unfavorable or unintended change in body structure (signs), body function (symptoms), laboratory result (eg, chemistry, ECG, X-ray, etc.), or worsening of a pre-existing condition associated temporally with the use of the study medication whether or not considered related to the study medication. Adverse events will be captured once a subject has signed the informed consent. AEs include:

- Changes in the general condition of the subject
- Subjective symptoms offered by or elicited from the subject
- Objective signs observed by the Investigator or other study personnel
- All concurrent diseases that occur after the start of the study, including any change in severity or frequency of pre-existing disease
- All clinically relevant laboratory abnormalities or physical findings that occur during the study

A treatment-emergent AE (TEAE) is any condition that was not present prior to treatment with study medication but appeared following treatment, was present at treatment initiation but worsened during treatment, or was present at treatment initiation but resolved and then reappeared while the individual was on treatment (regardless of the intensity of the AE when the treatment was initiated).

All AEs, including both observed or volunteered problems, complaints, signs or symptoms must be recorded on the AE page of the eCRF, regardless of whether associated with the use of study medication. This would include AEs resulting from concurrent illness, reactions to concurrent medication use, or progression of disease states (excluding the disease under study). A condition present at baseline that worsens after initiation of study treatment will be captured as an AE; the onset date will be the date the event worsened. The AE should be recorded in standard medical terminology when possible.

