17.6.4. Adverse Events

The Medical Dictionary for Regulatory Activities (MedDRA) will be used to code AEs.

An AE (classified by preferred term) that started on or after the date of the first dose of the study drug will be considered a TEAE if it was not present prior to the first dose of study drug, or was present prior to the first dose of study drug but increased in intensity during the treatment period. If more than 1 AE is reported prior to the first dose of study drug and coded to the same preferred term, then the AE with the greatest intensity will be used as the benchmark for comparison to the AEs occurring during the treatment period which were also coded to that preferred term. Any AE present prior to the first dose of study drug that increases in intensity during the treatment period will be re-entered with a new start date of the date of increased intensity.

Descriptive statistics (the number and percentage) for subjects reporting TEAEs will be tabulated by system organ class and preferred term; by system organ class, preferred term, and severity; and by system organ class, preferred term, and relationship to study drug. If more than 1 AE is coded to the same preferred term for the same subject, the subject will be counted only once for that preferred term using the most severe and most related occurrence for the summarization by severity and by relationship to the study drug.

Listings will be presented for all subjects. Additionally, listings will be presented for subjects with SAEs, subjects with AEs leading to discontinuation of study or study drug, and subjects who die (if any).

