3.2.6. Safety Parameters

3.2.6.1. Adverse Events

Adverse events will be mapped to preferred term using the Medical Dictionary for Regulatory Activities (MedDRA), Version 19.0. Treatment-emergent AEs are any AEs with a start date equal to or after the date of the first injection. Treatment-related AEs are any AEs with a relationship of possibly or probably related to study medication or AEs with a missing relationship.

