3.2.6.1.2. Adverse Event Duration

Duration of AEs will be the AE end date minus the AE start date + 1. Adverse event duration will be computed within each treatment session. Adverse events still ongoing at the end of the study or containing partial start or stop dates will not be included in the analysis of AE duration.

The duration of AEs will be used to determine the categories of AE durations (≥ 1 to ≤ 4 days, > 4 to ≤ 7 days, > 7 to ≤ 14 days, ≥ 15 to ≤ 21 days, and >21 days). For ongoing AEs, the category of AE duration will be missing unless those events have an onset date 21 days prior to the subject's last visit in the study. In this case, the category of the AE duration will be classified as " > 21 days".

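### The SAP's partial-date rules for AEs do not use the known stop date for treatment-emergent status, nor a provable minimum length in the duration analysis

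*SAP*

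**What the plan says.** **Treatment-emergent status.** SAP 3.2.6.1 defines the term by start date: "Treatment-emergent AEs are any AEs with a start date equal to or after the date of the first injection". Protocol 17.6.4 takes an AE that started on or after the first dose and says it "will be considered a TEAE if it was not present prior to the first dose of study drug", or if it was present earlier and then increased in intensity. For incomplete dates, SAP 3.5.3 imputes nothing for "partial AEs onset/end dates and partial concomitant medication start/stop dates" and gives a default: "All AEs with a missing onset day will be considered treatment emergent except if the onset month/year is prior to the first injection date". The next sentence of the same section handles medications differently and does look at the stop date: a medication lacking both days counts as concomitant unless its known stop month and year show that it ended before the first injection.

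**What is collected.** Protocol 14.1.1: "Adverse events will be captured once a subject has signed the informed consent". The synopsis gives "Screening Phase: Up to 14 days". SAP 3.1.9 records a resolution date, or ongoing, for every AE.

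**Duration.** SAP 3.2.6.1.2 computes stop date minus start date plus 1, and says that AEs "containing partial start or stop dates will not be included in the analysis of AE duration". It has one exception, repeated in 3.4.7.1.1: an ongoing AE with onset 21 days before the subject's last visit is placed in the > 21 days category. SAP 3.4.7.1.1 and 3.5.2 add up the durations of the same preferred term within a subject and treatment session, and the table classifies that sum.

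**The concern.** Each rule gives a wrong answer in a case where the recorded data already settle the matter.

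A default to treatment-emergent is reasonable when the order of onset and injection is unknown. If the stop date precedes the first injection, the order is known, and the AE satisfies neither definition of treatment-emergent. AEs are captured from consent, so such events can be in the database.

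For duration, the plan already accepts a lower bound for ongoing AEs: the exact length is unknown, but it is certainly over 21 days, so the category is assigned. A resolved AE whose partial dates prove the same thing is excluded.

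Safety is the primary objective and the study has a single arm, so no control column would carry the same error. Local injection-site reactions are the expected toxicity (Protocol 8.3), and their duration is a planned table (SAP 3.4.7.1).

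**Working it through.** The plan gives no figure to reproduce. The check applies the rules literally to example dates. The dates and the onset pattern are assumptions; the rules are the SAP's.

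**1. Treatment-emergent rule.** Take onset November 2017 with the day missing, stop date 15 Nov 2017, and first injection 20 Nov 2017.

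- Exception in 3.5.3: is the onset month/year before the injection date's month/year? November 2017 against November 2017: no.
- Result: treatment-emergent, although the AE ended 20 − 15 = 5 days before the injection.
- With a stop-date check (15 Nov before 20 Nov): not treatment-emergent.

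**2. How often the exception gives no protection.** Assume onset is equally likely on each of the 14 days before Day 1. If the injection falls on day d of the month, min(d − 1, 14) of those 14 days lie in the injection month. Averaging over d = 1 to 30:

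- d = 1 to 15 contributes 0 + 1 + … + 14 = 105
- d = 16 to 30 contributes 15 × 14 = 210
- (105 + 210) / (14 × 30) = 315 / 420 = 0.75

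A calendar enumeration gives 75.5% for injections from November 2017 to January 2018, and 75.3% over a full year. This is the share of pre-dose onsets falling in the injection month. It is not the share wrongly flagged: it includes events still present at injection, which a stop-date check leaves unchanged, and it matters only for AEs with no onset day.

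**3. Duration with a partial stop date.** Start 15 Jan 2018, stop March 2018 with the day missing.

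- Shortest: 1 Mar − 15 Jan + 1 = 46 days
- Longest: 31 Mar − 15 Jan + 1 = 76 days

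Every possible value exceeds 21 days, yet the AE is excluded. The ongoing-AE exception does not apply, because the AE has resolved.

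**4. Duration with a partial start date.** Suppose only the onset day is missing. The latest possible onset is the last day of the onset month, so the shortest possible duration is the true duration minus the days from true onset to month end. With onsets spread over one year, the share of such AEs provably over 21 days is:

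| True duration (days) | Provably > 21 days |
|---|---|
| 22 | 3% |
| 30 | 30% |
| 42 | 69% |
| 52 or more | 100% |

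The last row follows directly: at most 30 days separate onset from month end, and 52 − 30 = 22. These are shares of resolved AEs lacking only the onset day, not of all AEs.

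**5. What the table needs besides a duration.**

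- *Session.* SAP 3.2.6.1.1 assigns the session from the start date and has no rule for a partial one. With Day 1 on 20 Nov 2017, Day 22 is 11 Dec and Day 43 is 1 Jan 2018. A start of 15 Jan is clearly Session 3. A start in December with no day could be Session 1 or 2, so a bound on duration alone does not place it.
- *Summing.* Suppose a subject has two events of one preferred term in Session 3: one of 5 days with full dates (an illustrative value) and the event in step 3. Excluding the second leaves a sum of 5, in the > 4 to ≤ 7 days category. The shortest possible true sum is 5 + 46 = 51 days.

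**The case against.** The case for leaving the rules alone has several good points.

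- *The default is cautious.* It errs towards more treatment-emergent AEs, which suits a safety objective. That stands where timing is uncertain, but does not cover an event known to have ended before dosing.
- *The case is narrow.* It needs an onset after consent, a missing onset day, onset in the injection month, and a stop date known to precede injection. Conditions existing before screening go to medical history (Protocol 14.5.1), and missing data are queried (Protocol 22.1). This stands, and it is why the number is probably small.
- *Treatment-related tables are largely protected*, since they need a possible, probable or missing relationship. This stands: the first rule mainly affects the all-treatment-emergent tables.
- *Many long reactions are kept.* Ongoing AEs with a complete onset date far enough before the last visit go to > 21 days. This stands; the gap concerns resolved AEs. For an ongoing AE with a partial onset date, the text can be read either way.

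A reader might infer that the SAP ignores all known date parts, or that its exception rarely applies. Neither is supported: the known onset month is used, and under the assumption in step 2 the exception covers about 25% of pre-dose onsets.

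A reader might also infer that the duration table loses long reactions preferentially, because after the last post-treatment contact (Day 43 + 13 = Day 56 in the schedule of events) the next visits are Days 90 and 180, leaving stop dates to recall. That is plausible, but no section says that late stop dates more often lack a day. AEs are queried at every visit, and injection-site reactions are assessed at both late visits.

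**Conclusion.** The point holds as a minor one. SAP 3.5.3 can label as treatment-emergent an AE known to have ended before the first injection, which is inconsistent with SAP 3.2.6.1 and Protocol 17.6.4. SAP 3.2.6.1.2 drops resolved AEs whose recorded dates prove more than 21 days, although ongoing AEs are classified from just such a lower bound. No other section repairs either case.

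The direction is clear for the first rule: it can only overstate treatment-emergent counts. The second can understate long-lasting related reactions, but a systematic shortening of the table is inference. The size cannot be derived, because the frequency of partial AE dates is not given. The 75% rests on the even-onset assumption and says where the exception fails to help, not how many AEs are misclassified. No decision threshold in the plan depends on either rule.

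**What to change.** 1. **SAP 3.5.3.** Extend the AE exception with: *or if the recorded stop date (or stop month/year) is before the first injection date*. When the onset month is the injection month, a complete stop date is needed to decide. The month/year part helps only where the onset month is missing too. Where the order stays uncertain, the existing default remains.

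2. **SAP 3.2.6.1.2 and 3.4.7.1.1.** Where the treatment session can be determined, compute the shortest and longest durations that the known date parts allow, and sum each over events of the same SOC and preferred term in that session.
   - If the shortest sum exceeds 21 days, classify as > 21 days.
   - Otherwise, if both sums fall in one category, use it.
   - If not, show the subject in an unknown row.

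Both changes use data already collected. The cost is slightly more programming, mainly for summing the bounds, and one more row in the duration table.
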